11.1.2 Disease Parameters

Measurable disease. Measurable lesions are defined as those that can be accurately measured in at least one dimension (longest diameter to be recorded) as ≥ 10 mm by bidirectional measurements on oral examination. All lesion measurements must be recorded in millimeters (or decimal fractions of centimeters).

Non-measurable disease. All other lesions (or sites of leukoplakia), including small lesions (longest diameter < 10 mm), are considered non-measurable disease.

Target lesions. All measurable lesions up to a maximum of 3 lesions should be identified as **target lesions** and recorded and measured at baseline. Target lesions should be selected on the basis of their size (lesions with the longest diameter), be representative of the degree of high-risk oral leukoplakia, but in addition should be those that lend themselves to reproducible repeated measurements. It may be the case that, on occasion, the largest lesion does not lend itself to reproducible measurement in which circumstance the next largest lesion which can be measured reproducibly should be selected. A sum of the diameters (longest for all oral leukoplakia lesions) for all target lesions will be calculated and reported as the baseline sum diameters. The baseline sum diameters will be used as reference to further characterize any objective tumor regression in the measurable dimension of the disease.

Non-target lesions. All other lesions (or sites of leukoplakia) including any measurable lesions over and above the 3 target lesions should be identified as **non-target lesions** and should also be recorded at baseline. Measurements of these lesions are not required, but the presence, absence, or in rare cases unequivocal progression of each should be noted throughout follow-up.

11.1.3 Methods for Evaluation of Disease

All measurements should be taken and recorded in metric notation using a ruler or a digital (photographic) measurement tool. All baseline evaluations should be performed as closely as possible to the beginning of treatment and never more than 4 weeks before the beginning of the treatment.

The same method of assessment and the same technique should be used to characterize each identified and reported lesion at baseline and during follow-up. Color photographs of target lesions is preferred at each follow-up visit to accompany measurements.

11.1.4 Response Criteria

11.1.4.1 Evaluation of Target Lesions

STEP 1: Grade each individual lesion by size and histology to achieve the individual score of each site (up to 3 per patient).

Size	Criteria
L1	A lesion measuring < 2 cm in largest diameter
L2	A lesion measuring 2-3 cm in largest diameter
L3	A lesion measuring > 3 cm in largest diameter

Histology Criteria

P0 Keratosis of unknown significance with or without mild atypia (hyperkeratosis should not be reactive, such as from friction or factitial injury)

P1 Mild dysplasia

P2 Moderate dysplasia

P3 Severe dysplasia

Examples:

Patient A has 3 sites (1 cm, mild dysplasia = L1P1; 2.5 cm, mild dysplasia = L2P1; 2 cm, severe dysplasia = L2P3)

Patient B has 1 site (4 cm, moderate dysplasia = L3P2)

STEP 2: Score the patients individual sites using the below grid. A higher score reflects more advanced disease.

Points	Composite of Size / Histology
2	L1 P0
4	L1 P1
6	L1 P2
8	L1 P3
12	L2 P0
14	L2 P1
16	L2 P2

18	L2 P3
22	L3 P0
24	L3 P1
26	L3 P2
28	L3 P3

Examples:

Patient A has 3 sites (L1P1 = 4; L2P1 = 16; L2P3 = 18; total points = 38 is the composite score)

Patient B has 1 site (L3P2 = 26; total points = 26 is the composite score)

STEP 3: Following nivolumab, repeat measurements and histologic assessments. Recalculate the above score for each patient to assess the change in the composite score. Then calculate the change over the total baseline composite score as a (%) to the first decimal place.

Examples:

Patient A has 3 sites now (1 cm, mild dysplasia = L1P1; 2 cm, no dysplasia = L2P0; 1 cm, mild dysplasia = L1P1)

Patient B has 1 site now (2 cm, moderate dysplasia = L2P2)

Patient A has 3 sites now (L1P1 = 4; L2P0 = 12; L1P1 = 4; total points = 20 is the new composite score)

Patient B has 1 site now (L2P2 = 16; total points = 16 is the new composite score)

Patient A has 3 sites ($38 - 20$ points = $\Delta 18$), $18/38 = 47.4\%$

Patient B has 1 site ($26 - 16$ points = $\Delta 10$), $10/26 = 38.5\%$

STEP 4: Using the difference in the composite score for each patient, match to the response grid below.

Definition Best Overall Response

A decrease of > 80% or more CR

A decrease of 40-80% PR

Neither PR or PD SD

An increase of 10% or more PD

Examples:

Patient A has 3 sites ($38 - 20$ points = $\Delta 18$), $18/38 = 47.4\%$, called PR

Patient B has 1 site ($26 - 16$ points = $\Delta 10$), $10/26 = 38.5\%$, called SD

Complete Response (CR): A decrease of >80% in the total composite score, for at least 4 weeks.

Partial Response (PR): A decrease of 40-80% in the total composite score.

Progressive Disease (PD): At least a 10% increase in the total composite score.

(Note: the appearance of one or more new lesions is also considered progression).

Stable Disease (SD): Neither sufficient shrinkage to qualify for PR nor sufficient increase to qualify for PD.

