13. STATISTICAL CONSIDERATIONS

The primary objective of this trial is to evaluate best overall response rate (CR+PR). A two-stage design (Simon's optimal design) will be used to minimize the number of patients enrolled. Sixteen eligible patients who start protocol treatment are to be accrued in the first stage. If there are ≤ 1 patients with disease in response, accrual to this trial will be closed with the expectation that there is little evidence that the response rate will reach 25%. The probability that the trial will close early is 51.5% if the true response rate is 10%. If there are >1 patients with disease in response, accrual will continue until a total of 33 eligible patients who start protocol treatment are entered. If there are > 5 patients with disease in response among 33 eligible patients who began protocol treatment, further testing of this regimen will be considered. If the true response rate is 25%, the probability of concluding the regimen is effective is 84.3%, if the true response rate is 10%, the probability of concluding the regimen is effective is 9.8%. Allowing for patients to be declared ineligible or to not start protocol treatment after registration, a total of 35 patients will be entered.

The primary efficacy population includes all eligible patients who begin protocol treatment. Best overall response will be summarized as a proportion with a corresponding exact 95% confidence interval (CI) (if the trial closes to accrual after the first stage), or a corresponding 95% (two-stage) CI if the trial closes to accrual after the second stage.

For secondary objectives:

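### Size enters the primary score as three 10-point classes with no minimum shrinkage, so a 1 mm change across a cut-off can count as a response

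*Combined protocol and SAP*

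**What the plan says.** Section 11.1.4.1, Step 1, puts each target lesion in L1 ("A lesion measuring < 2 cm in largest diameter"), L2 ("A lesion measuring 2-3 cm in largest diameter") or L3 ("A lesion measuring > 3 cm in largest diameter"), and in one of four histology grades, P0 to P3. Step 2 converts the pair to points: "Score the patients individual sites using the below grid. A higher score reflects more advanced disease". The grid runs 2/4/6/8 for L1, 12/14/16/18 for L2 and 22/24/26/28 for L3.

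Step 4 classifies the percentage fall in total points. CR is "A decrease of > 80% or more CR"; PR is "A decrease of 40-80% in the total composite score".

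Section 11.1.2 requires diameters to be recorded in millimetres and the longest diameters of the target lesions (at most three) to be summed: "The baseline sum diameters will be used as reference to further characterize any objective tumor regression in the measurable dimension of the disease". No threshold is attached to that sum, and it is absent from Step 4. Section 11.1.3 allows a ruler or a photographic tool, and states no error limit or repeat reading.

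CR+PR is the primary endpoint. Section 13 stops at 1 or fewer responses in 16 patients and calls the regimen effective at more than 5 in 33. It states that "if the true response rate is 10%, the probability of concluding the regimen is effective is 9.8" per cent.

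**The concern.** A class boundary turns a small difference in reading into 10 points. Low-scoring lesions have few points to lose, so 10 points can exceed 40% of the baseline total. Nothing in the response criteria asks whether the lesion shrank by more than measurement error. In the other direction, substantial shrinkage within a class earns nothing.

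At stake is what the CR+PR count means. The decision turns on very few responders (2 to pass stage 1, 6 to succeed), so one or two produced by re-reading a borderline lesion could change it.

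**Working it through.** **Inputs.** Grid and thresholds from 11.1.4.1; design from Section 13. Percentage fall = (baseline points - follow-up points) / baseline points.

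**The plan's own figures.** Patient B, 4 cm to 2 cm with moderate dysplasia unchanged: (26 - 16)/26 = 38.5%, SD, as printed. (Patient A's printed baseline of 38 does not follow from the grid, which gives 4 + 14 + 18 = 36. That is a separate slip and is not used here.) For the design, P(go) is the sum over x = 2 to 16 of P(Bin(16, p) = x) × P(Bin(17, p) ≥ 6 - x). This gives 9.8% at p = 0.10 and 84.3% at p = 0.25, both as stated.

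**Sole target lesion, 1 mm change, histology unchanged.**

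| Change | P0 | P1 | P2 | P3 |
|---|---|---|---|---|
| 20 to 19 mm (L2 to L1) | 10/12 = 83.3%, CR-level | 10/14 = 71.4%, PR | 10/16 = 62.5%, PR | 10/18 = 55.6%, PR |
| 31 to 30 mm (L3 to L2) | 10/22 = 45.5%, PR | 10/24 = 41.7%, PR | 10/26 = 38.5%, SD | 10/28 = 35.7%, SD |

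Six of the eight crossings are responses.

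**Several target lesions.** One downward crossing gives PR in 18 of 104 two-lesion and 20 of 728 three-lesion grid configurations, and SD in the rest. These count configurations, not patients. Three L2P0 lesions (36 points): one crossing 10/36 = 27.8%, SD; two 20/36 = 55.6%, PR; three 30/36 = 83.3%, CR-level.

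**Shrinkage that scores zero.** 30 to 20 mm (33% smaller) stays L2. 60 to 31 mm (29/60 = 48% smaller) stays L3. Halving scores 0% for a lesion above 60 mm (80 to 40 mm) or one already in L1 (18 to 9 mm). Halving a lesion of 31 to 60 mm drops at least one class.

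**Illustrative size of the noise.** The documents give no measurement error or lesion-size distribution, so these inputs are assumed: true diameter uniform over 10-45 mm; 50/30/20% of patients with 1/2/3 target lesions; histology uniform over P0-P3; no true change; independent normal error on each reading, rounded to 1 mm.

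| Measurement SD | Spurious CR+PR, one follow-up reading |
|---|---|
| 1 mm | about 1.6% |
| 2 mm | about 3.2% |
| 3 mm | about 4.8% |

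If a second follow-up reading must confirm, the SD 2 mm figure falls to about 1.5%. It does not vanish, because a lesion over-read at baseline tends to look smaller at every later visit.

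**Effect on the decision.** If 10% describes genuine responses only and the noise is added:
- p = 0.10 + 0.015 = 0.115: P(go) = 16.0%.
- p = 0.10 + 0.032 = 0.132: P(go) = 24.7%.

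If noise can act only on the 90% who would not otherwise respond, the first becomes p = 0.10 + 0.9 × 0.015 = 0.1135 and P(go) = 15.3%. The range is therefore roughly 15-25%, against 9.8%.

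**Effect of a shrinkage condition (SD 2 mm, one reading).** Requiring a 30% fall in the sum of longest diameters cuts 3.2% to about 0.1%. A 5 mm per-lesion floor leaves about 0.9%, and at SD 3 mm leaves 2.7% of the 4.8%.

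**The case against.** Four counter-arguments deserve weight.

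1. **Other rules limit size-only responses.** Section 11.1.4.1 requires CR to last at least 4 weeks, and the 11.1.4.4 table has a 4-week confirmation column, though how far it reaches PR is unclear. Section 11.1.4.4 also makes best response depend on meeting both size and histology criteria; read literally, that could bar a size-only response, and no printed example awards one. These rules soften the point, but none sets a minimum shrinkage. Patient B is a size-only change run through the grid, and is SD only because 38.5% is below 40%. The sentence and the grid need reconciling.

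2. **The CR case is unusual.** A patient with no dysplasia enters only under criterion 2, with four-quadrant disease, so other sites will usually remain. The 11.1.4.4 table then makes target CR an overall PR. This stands, but that PR still counts in CR+PR. The PR case needs nothing unusual: criterion 3 admits a single lesion with moderate dysplasia and no size floor, and 20 to 19 mm in that patient is 62.5%.

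3. **Coarse classes are a deliberate choice.** Section 11.1 describes the scheme as modified from a published one, and 11.1.2 already provides the sum of diameters. This bears on severity; it does not remove the effect.

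4. **The noise figures rest on assumptions.** They do. The lesion-count mix matters most, and Section 13 does not say whether its 10% already includes misclassification. Nor does the calculation subtract genuine regressions that the classes miss.

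A reader might infer that every 1 mm crossing is a response, or that halving any large lesion earns nothing. The grid supports neither: L3P2 and L3P3 crossings are SD, one crossing among several target lesions is usually SD, and Patient B's halved lesion loses 10 points.

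**Conclusion.** The point holds as a possibility built into the score. That a 1 mm crossing can be scored PR, or reach CR level, follows from the printed grid with no assumption about measurement error, as does the zero credit for 30 to 20 mm and 60 to 31 mm.

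How often this would happen is not known from the documents. The 1.6/3.2/4.8% spurious rates and the 15-25% false-positive range are illustrations under the assumed error, lesion sizes, lesion counts and histology. The range also requires that the 10% null exclude noise. A reader might infer that the trial's actual type I error is 25%; the documents do not support that. The stated 9.8% is correct for a 10% rate of scored responses. What is missing is assurance that scored responses are real shrinkage or real histological improvement.

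Severity: should-fix.

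**What to change.** - Keep the printed composite score as the stated decision endpoint for the 1/16 and 5/33 rules.
- In Section 13, prespecify a sensitivity analysis in which a CR or PR reached through a size-class drop also requires at least a 30% fall in the sum of longest diameters.
- Tabulate the percentage change in that sum for every patient. This also shows large regressions that the classes miss.
- State whether the conclusion from more than 5 responses in 33 holds under both versions.
- If the condition is instead written into the primary definition, say so explicitly and apply it to both decision rules.
- Reconcile the 11.1.4.4 sentence on size and histology criteria with the size-only use of the grid, and state whether PR needs confirmation.

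The cost is protocol wording and one table from data already collected. In the sensitivity version, a few borderline responders become stable disease.

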3. PARTICIPANT SELECTION

Participants must meet the following eligibility criteria on screening examination to be eligible to participate in the study:

Eligibility Criteria

3.1.1 Subject must have have a confirmed diagnosis of high-risk oral leukoplakia which is defined by *any of the following*:

- (1) Diagnosis of oral PVL with multifocal lesions (≥ 2) or contiguous lesions ≥ 3 cm or a single lesion ≥ 4 cm in largest diameter (at least one lesion with any degree of dysplasia)
- (2) Diagnosis of oral PVL without dysplasia on biopsy but with 4 oral cavity quadrant involvement
- (3) Diagnosis of leukoplakia in at least 1 lesion with moderate dysplasia (without a diagnosis of oral PVL) for which surgery is indicated, but not feasible or patient refused.
- (4) Diagnosis of erythroplakia or erythroleukoplakia with any degree of dysplasia for which surgery is indicated, but not feasible or patient refused.

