11. MEASUREMENT OF EFFECT

11.1 Measurement of Effect – OPVL lesions

For the purposes of this study, participants will be re-evaluated for change in the measurements of each oral leukoplakia site at every study visit following initial study drug dosing. In addition, re-biopsy of initial oral leukoplakia sites (up to 3 per patient) will be obtained at the end of treatment, and to development of invasive oral cancer up to 5 years from study registration. Timelines are described in *Section 10*.

Response will be measured by: (1) measuring the change in size of each oral leukoplakia lesion,

and (2) by assessing histopathological change (a change in the degree of dysplasia as defined by histologic features) [modified from Wan der Waal I, et al. *Oral Oncol* 2000; 36(3):264-6]. *See Response Criteria below.*

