11.1.4.4 Evaluation of Best Overall Response

The best overall response is the best response recorded from study registration until first disease progression/diagnosis of invasive OSCC (taking as reference for progressive disease the smallest measurements recorded since the treatment started). The patient's best response assignment will depend on the achievement of both measurement and histologic criteria.

Measurable Disease (*i.e.*, Target Disease)

Target Lesions	Non-Target Lesions	New Lesions	Overall Response	Best Overall Response when Confirmation is Required*
CR	CR	No	CR	≥ 4 wks Confirmation**
CR	Non-CR/Non-PD	No	PR	≥ 4 wks Confirmation**
CR	Not evaluated	No	PR	
PR	Non-CR/Non-PD/not	No	PR	

	evaluated				
SD	Non-CR/Non-PD/not evaluated	No	SD	Documented at least once \geq 4 weeks from baseline**	
PD	Any	Yes or No	PD	no prior SD, PR or CR	
Any	PD***	Yes or No	PD		
Any	Any	Yes	PD		

* See manuscript for further details on what is evidence of a new lesion.
 
** Only for non-randomized trials with response as primary endpoint.
 
*** In exceptional circumstances, unequivocal progression in non-target lesions may be accepted as disease progression.
					

Note: Participants with a global deterioration of health status requiring discontinuation of treatment without objective evidence of disease progression at that time should be reported as “symptomatic deterioration.” Every effort should be made to document the objective progression even after discontinuation of treatment.
					

Non-Measurable Disease (*i.e.*, Non-Target Disease)

Non-Target Lesions	New Lesions	Overall Response
CR	No	CR
Non-CR/non-PD	No	Non-CR/non-PD*
Not all evaluated	No	Not evaluated
Unequivocal PD	Yes or No	PD
Any	Yes	PD

* ‘Non-CR/non-PD’ is preferred over ‘stable disease’ for non-target disease since SD is increasingly used as an endpoint for assessment of efficacy in some trials so to assign this category when no lesions can be measured is not advised.

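### The composite response score can give a PR when dysplasia has worsened; its worked example disagrees with its grid, and an absent lesion has no score

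*Combined protocol and SAP*

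**What the plan says.** Section 11.1 names two components of response. It begins "Response will be measured by: (1) measuring the change in size of each oral leukoplakia lesion" and then adds change in the degree of dysplasia.

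Section 11.1.4.1 combines them. Each target lesion gets a size class (L1 to L3) and a histology grade (P0 to P3), each pair has a printed point value, and the points are summed per patient. Step 4 reads "Using the difference in the composite score for each patient, match to the response grid below", and the definitions that follow use the same total: "Partial Response (PR): A decrease of 40-80% in the total composite score". CR needs a fall of more than 80% held for at least 4 weeks; PD is a rise of at least 10%.

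Section 11.1.4.4 adds that the patient's "best response assignment will depend on the achievement of both measurement and histologic criteria". Neither section gives a separate threshold for size or for histology, and the table in 11.1.4.4 has no histology entry.

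The Step 2 example for Patient A is scored "L1P1 = 4; L2P1 = 16; L2P3 = 18; total points = 38". The grid just above it gives L2P1 14 points.

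Section 13 makes CR+PR the primary endpoint, with decisions at more than 1 of 16 and more than 5 of 33.

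**The concern.** Because size and histology are added, a large fall in size can pay for a rise in dysplasia. The primary objective (1.2) concerns efficacy on both measurement and degree of dysplasia, and 11.1.4.4 speaks of achieving both. A patient whose mild dysplasia became severe fits neither well, yet can be counted as a PR. The reported CR/PR/SD/PD categories would not reveal it.

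The other two problems affect whether assessors obtain the same score at all. One cell of the grid has two values, depending on whether the assessor follows the table or the example. A lesion that is gone has no value. Either can change a category, and the categories feed the only primary endpoint.

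**Working it through.** **Inputs (11.1.4.1, Step 2 grid).** L1 P0-P3 = 2, 4, 6, 8; L2 P0-P3 = 12, 14, 16, 18; L3 P0-P3 = 22, 24, 26, 28. One size class is worth 10 points and one grade 2, so the whole histology range (P0 to P3) is worth 6. Percent decrease = (baseline − new) / baseline.

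**Plan's own figure.** Patient B, L3P2 to L2P2: (26 − 16)/26 = 38.5%, SD. This reproduces.

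**1. Worse dysplasia with a PR.** I crossed every single-lesion baseline with P1-P3 against all 12 follow-up cells. Six transitions reach at least 40% with a higher grade than at baseline:

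| Baseline | Follow-up | Points | Decrease |
|---|---|---|---|
| L2P1 | L1P2 | 14 to 6 | 57.1% |
| L2P1 | L1P3 | 14 to 8 | 42.9% |
| L2P2 | L1P3 | 16 to 8 | 50.0% |
| L3P1 | L1P2 | 24 to 6 | 75.0% |
| L3P1 | L1P3 | 24 to 8 | 66.7% |
| L3P2 | L1P3 | 26 to 8 | 69.2% |

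- All six are PR and all end below 2 cm. Stopping at L2 is not enough: L3P1 to L2P2 is 8/24 = 33.3%, and L3P2 to L2P3 is 8/26 = 30.8%.
- All six baselines are eligible under 3.1.1. The L3 lesions can enter under criterion 1, "in largest diameter (at least one lesion with any degree of dysplasia"; L2P2 under criterion 3 or 4; L2P1 under criterion 4, "Diagnosis of erythroplakia or erythroleukoplakia with any degree of dysplasia".
- Several targets do not prevent it: two L2P1 lesions that both become L1P3 go from 28 to 16, 12/28 = 42.9%, PR.
- From P0 baselines there are five more such cells. One exceeds 80%: L3P0 to L1P1, 22 to 4, 81.8%.

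**2. L2P1 = 14 or 16.** Patient A's baseline is 38 as printed and 4 + 14 + 18 = 36 on the grid. The new score is 20, so the decrease is 18/38 = 47.4% or 16/36 = 44.4%, PR either way. Other transitions do change category:

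| Transition | L2P1 = 14 | L2P1 = 16 |
|---|---|---|
| L3P1 to L2P1 | 10/24 = 41.7%, PR | 8/24 = 33.3%, SD |
| L3P2 to L2P1 | 12/26 = 46.2%, PR | 10/26 = 38.5%, SD |
| L2P1 to L2P2 | rise 2/14 = 14.3%, PD | 0%, SD |

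**3. Absent target.** The lowest printed value is 2.
- If absence is scored as L1P0, the largest fall for a patient whose targets are all under 2 cm is from P3: (8 − 2)/8 = 75.0%, so CR is out of reach. If those targets are all P0, the change is (2 − 2)/2 = 0%, SD.
- If absence adds nothing to the sum, the same patients reach 100%.

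**Where one patient could matter.** The two-stage rule reproduces: 9.8% at a true rate of 10% and 84.3% at 25%. The first-stage count is exactly 2 of 16 with probability 120·p²(1 − p)¹⁴ = 27.5% (p = 0.10) or 13.4% (p = 0.25). The trial continues and ends at exactly 6 of 33 with probability 5.8% or 10.3%. These are chances of sitting on a boundary, not of a changed decision.

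**The case against.** The strongest reply is that nothing contradicts: the composite is the rule, and the phrase in 11.1.4.4 refers to its two inputs. There is good support for this. Step 1 prints its histology table under a heading that calls it criteria. The result column in Step 4 is labelled as best overall response. The table in 11.1.4.4 takes target-lesion status from 11.1.4.1, where histology is already counted, so it needs no histology column. Both examples follow the score alone: Patient B is SD only because 38.5% is below 40%, and Patient A is called PR although one site is unchanged and another stays in its size class.

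This largely stands. A reader might infer that the two sections conflict outright and that each domain must improve separately. The documents do not support that. No separate thresholds exist, and such a rule would make response impossible for patients whose targets are all P0, whom criterion 2 admits: "Diagnosis of oral PVL without dysplasia on biopsy but with 4 oral cavity quadrant involvement". A response that improves one domain while the other is unchanged is therefore not a defect.

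It is also fair that the weighting is openly printed and is a design choice, and that the absent-lesion gap is narrow: scored as L1P0, a vanished L2P0 lesion still reaches 10/12 = 83.3%.

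The reply does not cover worsening. No sentence says that the composite is what 11.1.4.4 means, and achieving a histologic criterion is hard to square with mild dysplasia becoming severe. Nor does it answer the two values for L2P1 or the missing score.

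**Conclusion.** The point holds as a gap in definition and reporting. On the most natural reading, PR can be assigned when dysplasia has risen, and the planned summaries would not show it. The Patient A discrepancy is more than a typing slip, because the value of L2P1 decides PR against SD, and SD against PD, for other patients. The missing score for an absent lesion can decide CR for patients with only small targets, and response itself where those targets are all P0.

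The size is limited. The printed grid has 35 single-lesion CR/PR transitions from a dysplastic baseline, six of them with worse dysplasia. A reader might take this as the share of responders affected, or as evidence that the 9.8% type I error is wrong. Neither follows: these are grid cells, all six need shrinkage to below 2 cm, and the documents say nothing about how often that occurs together with a higher grade. The effect on the observed rate and on the error rates cannot be derived. One reclassified patient alters a decision only at 2 of 16 or 6 of 33.

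The counts assume the grid as printed. With L2P1 = 16, the six cells remain PR. This should be fixed before responses are counted.

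**What to change.** 1. Keep the composite as the primary rule and say so in 11.1.4.4, for example: *Target-lesion response is assigned from the composite score in 11.1.4.1; that score is how the measurement and histologic criteria are jointly applied.* Beside CR+PR, pre-specify a count that excludes patients with a higher dysplasia grade than baseline in any target. Add separate size and histologic response rates, with their thresholds fixed in advance, from the lesion measurements and re-biopsies already planned.
2. Reconcile the grid with the Patient A example. If the grid stands, the example becomes L2P1 = 14, 36 to 20 points, 44.4%, PR.
3. Give a score for a target that is clinically absent with a clear planned re-biopsy. Zero is the natural value; the sponsor should confirm it.

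**Cost.** Some wording and a little more analysis; no new patients, visits or biopsies. Scoring absence as 0 rather than as L1P0 may add some responders among patients with only small lesions, so it should be settled before any responses are tallied.
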